- 1. Control Group: All control group participants will follow the ACL reconstruction rehabilitation protocol These patients will complete outcome measures, and standardized strength assessments consistent with the standard current standard of care listed above. The same data points will be collected.
- 2. All data collected all time points will be stored in a custom built REDcap database built specifically for this study.

Recruitment and Retention: We will track recruitment and retention as outcomes. Connecticut Children's sports medicine surgeons and physical therapists care for approximately 100-150 ACL tears per year on average. Our expertise in pediatric sports medicine positions us well to treat these patients after ACLR. Our physical therapists will care for approximately half of these patients on an annual basis. In our recent pilot study, we enrolled approximately 40 patients and had 0% attrition in our BFRT group throughout the study period. Our close relationship and adjoined clinic with our sports medicine providers allows us to target and recruit potential patients for enrollment. Our team has been able to identify and establish formal procedures for the recruitment and consenting process. We anticipate to enroll 2-4 patients/month, and at this rate we would finish enrollment within approximately 10 months.

Study Procedures: All patients that undergo ACLR at Connecticut Children's begin physical therapy within 5-7 days of surgery. The implementation of BFRT will begin at the **second** post-operative visit to account for differences in post-operative pain and recovery.

BFRT Intervention Group:

In addition to the standard ACL rehabilitation protocol, the experimental group will complete 2 exercises using the Delfi BFR cuff 2x/week for 8 weeks during their treatment session at Connecticut Children's Sports Physical Therapy on the second post-operative visit. Exercise selection is listed in Table 2. All patients will use the Delfi BFR unit and will complete exercises at 80% limb occlusion pressure. Cuff size will be determined by patient thigh circumference as described in Delfi BFR unit manual. Limb occlusion pressure will be determined in supine position and all exercises will be completed at 80% occlusion.

Control Group: In addition to the standard ACL rehabilitation protocol, the control group will complete the same exercises as the experimental group starting on the second post-operative visit.

Table 2. Exercise Progre	ession	

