- c. For the long arc quadriceps (LAQ) progression, all exercises will start with no external resistance and after every 2 sessions weight will be increased by 1 pound. For the Shuttle progression, exercises will start at 30% of patients 1RM. An estimated single leg and double leg 1 repetition max will be determined at pre-operative visit. Patients unable to complete the prescribed dosage will complete the exercise using both limbs on the Shuttle and will use a ratings of perceived exertion (RPE) scale to determine intensity. RPE has been shown to be an effective tool to individualize exercise prescription and load progression.⁵⁶
- d. The standing straight leg raise exercise will be completed from week 0-2 unless the patient is able to demonstrate 10 straight leg raise repetitions with minimal extensor lag. All standing exercises will be standardized to complete in the same position to have minimal compensation.
- e. Discontinuation or stoppage of exercise: Patients will be instructed to attempt to complete all exercises. Should the patient be unable to tolerate 80% limb occlusion or report lower extremity paresthesia, the therapist will reduce occlusion by 5mmHg between exercise sets. Should the patient reach less than 60% limb occlusion, the exercise will be stopped.
- f. At the completion of both exercises, patients will be asked to rate RPE, pain on a visual analog scale, and report from a list of documented adverse events.

Control Group: All exercises will be completed in the manner described above without the use of the Delfi BFR device. Exercise volume, progression, and discontinuation will be determined in the same manner.

Sample Size/Power Analysis: Based on our preliminary work evaluating differences between isometric quadriceps strength at 3 and 6 months after ACLR in adolescents, an a priori power analysis for a two-way Version 1.2_.1.8.2023

repeated measures analysis of variance (within-between interaction) was conducted using an alpha level of 0.05, power of 0.80 and moderate effect size (0.6). The projected sample size needed to determine differences between groups was determined to be 14 total individuals. Thus, we have increased the sample size to 40 (20 per group) to allow for even group numbers and to account for possible attrition.

Data analysis

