Data will be collected on all patients enrolled into the study. Descriptive statistics will be generated on the demographic characteristics of both treatment groups. We will use a two-way repeated measures analysis of variance to determine the effect of treatment groups, BFRT compared to standard of care therapy, over time on subjective and objective outcomes. Exact analysis for each test will depend on variance and distribution/normality of data set. This will be achieved using the Statistical Package for the Social Sciences (SPSS) software version 27.0 (IBM Corp., Armonk, NY, USA). We will address each aim in the following manner.

Accrual and Expected Duration of Accrual

Once approved, we expect that this study can be accomplished within two to three years. The open period for this study will be between February 2022 and February 2025.

Study Limitations:

There are several limitations anticipated with this study that will impact its power and external validity. These limitations include an inherent sampling bias with our recruitment strategy, lack of patient or participant blinding, and small sample size.

Attempts will be made to reduce any potential bias by having standardized educational scripts regarding BFR training that each treating therapist will read to subjects prior to their first BFR session.

Subjects in our study will likely come from the same surgeons and the same type of ACL graft (QT). This could be a potential limitation in the generalizability of our results to other surgeons and graft types.

Administrative Organization

Roles and responsibilities:

[name], PT, DPT: Will serve as the study's primary investigator. [name] will provide primary support for the SRC and IRB study protocol development and submission, as well as maintaining updates and compliance with clinicaltrials.gov. He will review the required databases and pull the relevant data required to complete this study. He will also aid in data interpretation and manuscript preparation.

All MDs listed: The MDs listed on this proposal will be responsible for recruitment of patients, data interpretation and manuscript preparation.

All physical therapists listed: The PT's listed on this proposal will serve as the study's co-investigator. They will provide support in development of SRC and IRB documents (review of literature). They will help with data collection, recruitment, consenting patients.

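### The sample size calculation calls 0.6 a moderate effect, but on the scale of the named test 0.6 is well above large, so the claim that 14 patients suffice for a moderate effect is not supported

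*Protocol*

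**What the plan says.** Under Sample Size/Power Analysis, the protocol bases its calculation on pilot isometric strength at 3 and 6 months. The test is a two-way repeated measures ANOVA, for the within-between interaction, "conducted using an alpha level of 0.05, power of 0.80 and moderate effect size (0.6"). The result is 14 patients in total. The protocol then says it has "increased the sample size to 40 (20 per group) to allow for even group numbers and to account for possible attrition".

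It does not give the effect-size scale, the number of repeated measurements entered, the correlation between them or a dropout rate.

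Two other places bear on this. Recruitment and Retention reports that the pilot "had 0% attrition in our BFRT group throughout the study period". Study Limitations includes small sample size among the "limitations anticipated with this study that will impact its power and external validity".

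**The concern.** The label and the number do not fit together for the test that is named. Power for a within-between interaction is computed from Cohen's f. By the usual convention (a convention of the method, not a figure in the protocol), f = 0.25 is medium and f = 0.40 is large. A value of 0.6 is 1.5 times large. The word moderate suits 0.6 only on the scale of Cohen's d.

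This paragraph is the only justification given for the trial's size. A reader will take from it that a moderate effect can be detected with 14 patients and that 40 leaves ample room for loss. A null result could then be read as excluding a moderate effect on the strength of a calculation that was probably run for a much larger one.

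A second, independent weakness is that the reasons given for going from 14 to 40 do not account for the size of that step.

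**Working it through.** **Inputs from the protocol.** Alpha 0.05, power 0.80, effect size 0.6, k = 2 arms of equal size, and 14 then 40 patients (Sample Size/Power Analysis). The pilot basis of 3 and 6 months suggests m = 2 measurements. The trial itself plans five assessment points (Data Collection).

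**Assumed, because not stated.** Correlation ρ between visits (shown as a range), number of measurements m (2 or 5), and sphericity.

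**Formula.** Noncentral F for the interaction: df1 = m − 1, df2 = (N − 2)(m − 1), λ = f² × N × m / (1 − ρ). N is rounded up to an even number.

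**Step 1: reproduce the stated 14.** Take f = 0.6, m = 2, ρ = 0.
- N = 12: λ = 0.36 × 12 × 2 = 8.64, power 0.755.
- N = 14: λ = 0.36 × 14 × 2 = 10.08 on (1, 12) df, power 0.830.

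So 14 is the smallest even N that reaches 0.80. With ρ = 0.5 the same f would need only 8.

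**Step 2: what f = 0.6 means here.** With two arms and two visits, a difference D between arms in mean change (in within-visit SD units) puts an interaction effect of D/4 in each cell, so f = D/4. Hence D = 4 × 0.6 = 2.4 SD.

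**Step 3: a medium effect, f = 0.25, two visits.**

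| ρ | λ at N = 14 | Power, N = 14 | N for 80% | Power, N = 40 |
|---|---|---|---|---|
| 0 | 1.75 | 0.23 | 66 | 0.59 |
| 0.5 | 3.50 | 0.41 | 34 | 0.87 |
| 0.7 | 5.83 | 0.60 | 22 | 0.98 |

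With five visits, f = 0.25 and N = 40, power is 0.81 at ρ = 0 and 0.99 at ρ = 0.5.

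**Step 4: other routes to 14.**
- If 0.6 is d, the usual conversion f = d/2 gives f = 0.3. With two visits and ρ = 0.75, λ = 0.09 × 14 × 2 / 0.25 = 10.08, the same as in Step 1, so N = 14 with power 0.830.
- f = 0.25 with five visits and ρ = 0.7 also gives N = 14.

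**Step 5: from 14 to 40.** If attrition alone explained the increase, the loss allowed for would be 1 − 14/40 = 26/40 = 65%. An even split does not need more patients, since 14 = 7 + 7.

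**Step 6: what 40 detects, for illustration.** Solve for the f that gives 80% power with two visits, then D = 4f.

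| Evaluable N | ρ = 0.5 | ρ = 0.7 |
|---|---|---|
| 40 | 0.91 SD | 0.70 SD |
| 32 | 1.02 SD | 0.79 SD |

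**The case against.** The best defence is that no sum is wrong. Fourteen follows from 0.6 entered as f, and it can also be right for a moderate effect: f = 0.3 (d = 0.6 converted) with two visits and correlation 0.75 gives exactly 14, as does f = 0.25 with five visits and correlation 0.7. The 2.4 SD reading is also conditional. It needs 0.6 as f, two visits, and f defined on the within-visit SD; under the partial-eta-squared convention used in SPSS, f = 0.6 with four visits gives 14 too. All of this stands. It means that 14 cannot be called an arithmetic error or shown to be wrong. It does not rescue the paragraph, because the routes that make 14 right for a moderate effect depend on inputs that the protocol does not state.

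A reader might go further and infer that 40 patients are too few. The protocol does not support that: at f = 0.25, 40 patients give power of 0.59 to 0.99 over the cases in the working, and of the tabulated cases only two visits with zero correlation falls short of 0.80.

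A reader might also infer that the plan expects to lose most of its patients. It does not say so; it mentions possible attrition without a rate, and 65% is only what the step from 14 to 40 would imply. The pilot's 0% covers the BFRT arm alone, and this trial can lose patients through its 80% attendance rule and its exclusion for follow-up surgery. Nor does the attrition point follow from the effect-size label; it stands by itself.

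Finally, small sample size under Study Limitations may look like a contradiction of a stated need for 14. It is one item in a general list of cautions and contradicts nothing.

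**Conclusion.** The point holds as a fault in how the effect size is labelled and scaled. For the named test, 0.6 is well above large, so the stated 80% power for a moderate effect with 14 patients is not supported as written. On the two-visit basis that the pilot suggests, a medium effect gives 14 patients about 23% to 60% power over correlations of 0 to 0.7, and needs 66 down to 22 patients. These figures rest on the conventional benchmarks for f, on two visits and on the assumed correlations. At higher correlation or with more visits, 14 can be enough.

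Separately, the stated reasons for enlarging 14 to 40 do not explain the increase. Neither point shows that 40 is inadequate.

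**What to change.** Keep 40 patients and rewrite the Sample Size/Power Analysis paragraph.

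- Replace the moderate effect size of 0.6 and the figure of 14 with an effect on a named scale (f, or SD, or Nm/kg), the number of visits in the calculation and the assumed correlation.
- State the effect that 40 patients detect with 80% power under those inputs. The two-visit figures in Step 6 show the form such a statement would take; the sponsor should recompute them from the pilot's own correlation and SD.
- Replace the sentence on even groups and attrition with an explicit dropout allowance and the evaluable number that it leaves. For example, at f = 0.25, two visits and correlation 0.5, the N needed is 34, so 40 allows a loss of 6 (6/40 = 15%).

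The cost is one rewritten paragraph with less favourable figures than the present one. No extra patients are needed.

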Once identified as a potential candidate, the study purpose and protocol will be explained and a brief summary of the study will be provided at the conclusion of the pre-operative appointment. Patients must meet all the requirements of inclusion and exclusion criteria to be eligible for consent.

Consent: Consenting will take place at the pre-operative visit. The patient/parent will be given a detailed description of the purpose and methodology for this study. They will have the opportunity to read the consent forms and ask any questions they may have about the research. If they agree to participate, they will be asked to sign the consent form and a copy will be provided to the patient and family. All consenting documents will be stored in REDCap

If patients agree to enroll, all demographics and information listed in the protocol will be stored in REDCap on a data collection sheet that is listed in the attachments. This sheet will be used to record all pertinent information for all active participants on the study and will be stored in REDCap

Retention: Eligible patients will be required to be seen for a minimum of 80% of patient visits to be included in this study.

Data Collection:

Prior to completing enrollment measures, patients will provide written informed consent to participate in the study. Data collection will occur at five different time points during the rehabilitation process: preoperatively, 8 weeks, 12 weeks, 6 months, and time of return to play. Return to play assessments will be completed at approximately 9 months post-operatively. The schedule of study assessments is listed in Table 1 below.

Table 1. Schedule of Study Procedures and Assessments						
Procedure	Pre-operative	8	12	6	Return	2 year
	Screen	weeks	weeks	months	to Play	follow-up
Informed Consent	x					
Background Information	x					
Patient Reported Outcomes	x	Х	х	х	х	x
Estimated 1 rep Max	X					
Mid-thigh circumference	X	х	Х	х	х	
Isometric thigh strength	X	Х	х	х	Х	
Isokinetic thigh strength				х	х	
Range of motion (ROM)	X	X***	х	х	х	
***ROM will be assessed and collected at each treatment visit for the first 8 weeks after surgery						

Primary Outcomes (See table below):

Active knee range of motion: Knee AROM will be measured in supine position using a goniometer and standardized procedures reported by Norkin and White.³⁵

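### The one named analysis, a two-way repeated-measures ANOVA, keeps only patients with every visit in the model; a mixed model in the same software would keep all randomised patients

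*Protocol*

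**What the plan says.** The Data analysis section gives one inferential method for both subjective and objective outcomes: "We will use a two-way repeated measures analysis of variance to determine the effect of treatment groups". The software is "Statistical Package for the Social Sciences (SPSS) software version 27.0". The only stated flexibility is "Exact analysis for each test will depend on variance and distribution/normality of data set", which concerns the shape of the data and not missed visits. The section ends by announcing an aim-by-aim description, which does not follow.

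The same family of test is used in Sample Size/Power Analysis: "repeated measures analysis of variance (within-between interaction) was conducted using an alpha level of 0.05". That calculation gives 14 patients, raised to 40 (20 per group) "to allow for even group numbers and to account for possible attrition".

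The Data Collection section schedules assessments "preoperatively, 8 weeks, 12 weeks, 6 months, and time of return to play". Table 1 places isometric strength and mid-thigh circumference at all five and isokinetic strength at the last two. Questionnaires have an additional 2-year contact. The Data analysis section opens with "Data will be collected on all patients enrolled into the study".

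Two other places make attendance a condition of inclusion. The exclusion criteria refer to attending all assessment visits, and the Retention paragraph requires at least 80% of visits.

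**The concern.** Classical repeated-measures ANOVA, as run in the SPSS repeated-measures procedure, needs a complete set of visits for each patient. One missing value removes that patient from the whole analysis of that outcome, including the visits that were attended.

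Hypotheses 1a and 1c concern the pre-operative, 8-week and 12-week measurements. If one five-visit model is fitted, who counts in those early comparisons depends on who also came at 6 months and at about 9 months. In a 40-patient trial this discards data the protocol sets out to collect, and it lowers precision. If attendance is related to how the knee is doing, the patients left are no longer quite the groups that were randomised.

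This concerns a method the protocol fixes, not a detail it leaves open: the named test determines what happens to an incomplete patient, and a test without this property is available in the same software.

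**Working it through.** **1. The protocol's own figure.** Inputs from Sample Size/Power Analysis: "an alpha level of 0.05, power of 0.80 and moderate effect size (0.6"), two groups, within-between interaction. The number of measurements m and the correlation rho are not stated. I assume m = 2, because the effect is said to come from strength at 3 and 6 months, and rho = 0.

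Noncentrality λ = f² × N × m / (1 − rho), with df1 = m − 1 and df2 = (N − 2)(m − 1).

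- N = 12: λ = 0.36 × 12 × 2 = 8.64, power 0.75
- N = 14: λ = 0.36 × 14 × 2 = 10.08, power 0.83

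So 14 is the smallest even total reaching 0.80, and the stated figure reproduces on those assumptions.

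**2. Patients left by complete-case analysis.** No missed-visit rate is given, so I assume a rate p at each post-operative visit, independent between visits, with the pre-operative value always present. Expected complete cases = 40 × (1 − p)^v, where v is the number of post-operative visits in the model.

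| Visits in the model | p = 5% | p = 10% |
|---|---|---|
| All five (v = 4) | 40 × 0.95⁴ = 32.6 | 40 × 0.90⁴ = 26.2 |
| Pre-op, 8 and 12 weeks (v = 2) | 40 × 0.95² = 36.1 | 40 × 0.90² = 32.4 |

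A mixed model keeps all 40, since each has at least the pre-operative value.

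**3. Power on the protocol's effect size** (f = 0.6, m = 2, rho = 0).

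- N = 40: λ = 28.8, power 0.999
- N = 26: λ = 18.72, power 0.986

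**4. Power on a smaller interaction effect** (assumed f = 0.25, m = 2, rho = 0.5, so λ = 0.25 × N).

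- N = 40: λ = 10, power 0.87
- N = 32: λ = 8, power 0.78
- N = 26: λ = 6.5, power 0.69

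**5. Complete cases against all available data.** Simulation with 20 per arm, five visits, an arm difference of 0.6 SD at every post-operative visit, correlation 0.6 between any two visits, and visits missed at random. The test is the arm difference in mean post-operative value minus pre-operative value, with 1,500 runs per setting. The 0.6 SD here is a mean difference, a different scale from the protocol's f = 0.6.

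| Missed per visit | Mean complete cases | Power, complete cases | Power, all available |
|---|---|---|---|
| 0% | 40.0 | 0.73 | 0.74 |
| 5% | 32.5 | 0.65 | 0.74 |
| 10% | 26.1 | 0.52 | 0.70 |

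Monte Carlo error is about 1.2 percentage points. The all-available analysis used the true covariance, so its power is slightly optimistic.

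**6. Bias.** Same setting, but weaker control patients miss visits more often (base rate 5% to 10%). With a true difference of 0.60 SD, complete cases give about 0.56 and all available data about 0.59 to 0.60. With a true difference of zero, complete cases give about −0.03 to −0.06 SD and all available data about zero.

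**The case against.** The strongest reply is that one model over all visits is an inference. The protocol does not say which visits enter each analysis, and the hypotheses name their own: 8 and 12 weeks for 1a, 6 months and return to sport for 1b, pre-operative to 8 weeks for 1c. If each is tested on its own visits, missing the 9-month test removes nobody from 1a or 1c. This stands. It is why the 36 or 32 figures are shown beside 33 or 26, and the power loss is correspondingly smaller.

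Second, the trial has room. On the protocol's own effect size 26 complete patients still give power of 0.986. The pilot had no attrition in its BFRT group, and assessments coincide with surgeon visits. This also stands, with two limits: no pilot figure is given for controls, and the spare power disappears if the true effect is smaller.

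Third, the attendance conditions may remove many of the same patients before any model is fitted. That is correct. Changing the model alone is therefore not enough.

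A reader might go further on three points that the document does not support:

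- *Failure to answer at 2 years would shrink the questionnaire analysis.* No section places the 2-year contact in the ANOVA, and it is described as additional.
- *The test would reject too often because correlations between visits are unequal.* Nothing says the test will be uncorrected, SPSS supplies corrections, and with two visits the issue cannot arise.
- *Complete-case results would be seriously biased.* Even under deliberately outcome-related missingness the shift was a few hundredths of an SD.

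**Conclusion.** The point holds as a worthwhile improvement. It does not show that the trial will fail. The named method discards every patient incomplete on the visits entered, in a protocol that plans for attrition, and a better method costs almost nothing.

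The size is uncertain. Between about 4 and 14 of 40 patients would be lost (40 − 36 and 40 − 26), depending on an assumed 5% or 10% missed-visit rate and on which visits are modelled. The power cost is negligible at f = 0.6. At an assumed 0.6 SD with correlation 0.6 and all five visits modelled, it is roughly 9 percentage points (0.74 to 0.65) or 18 (0.70 to 0.52). The loss of randomised patients does not depend on the effect size.

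**What to change.** Replace the ANOVA sentence in the Data analysis section with wording along these lines: each continuous outcome is analysed by a linear mixed model for repeated measures (SPSS MIXED, REML) with arm, visit and arm-by-visit terms and an unstructured within-patient covariance. If that does not converge, heterogeneous compound symmetry is used. Degrees of freedom use a small-sample method such as Satterthwaite. All observed visits of all randomised patients are included.

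Then:

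- State the contrast for each hypothesis: arm difference in isometric outcomes at 8 and at 12 weeks (1a), in isokinetic outcomes at 6 months and return to sport (1b), and in change from pre-operative to 8 weeks (1c).
- Keep the complete-case repeated-measures ANOVA as a labelled sensitivity analysis.
- State that the all-assessment-visits condition in the exclusion criteria and the 80% condition under Retention do not remove randomised patients from this analysis.

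The mixed model is valid if missingness depends only on observed data, and should give much the same answer if nobody misses a visit. The cost is about a paragraph of protocol or SAP text, slightly more analysis work and approximate degrees of freedom. No new data, software or patients are needed.
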